11.6.2 Study Records Retention

To enable evaluations and/or audits from regulatory authorities or the sponsor, the investigator agrees to keep records, including the identity of all participating subjects (sufficient information to link records, e.g., case report forms (CRFs) and hospital records), all original signed ICFs, copies of all eCRFs, SAE forms, source documents, detailed records of drug disposition, and adequate documentation of relevant correspondence (e.g., letters, meeting minutes, and

telephone calls reports). The records will be retained by the investigator according to the ICH, local regulations, or as specified in the Clinical Study Agreement, whichever is longer.

If the investigator becomes unable for any reason to continue to retain study records for the required period (e.g., retirement and relocation), the sponsor will be prospectively notified. The study records will be transferred to a designee acceptable to the sponsor, such as another investigator, another institution, or to the sponsor. The investigator will obtain sponsor's written permission before disposing of any records, even if retention requirements have been met.

11.7 Reporting of Safety Issues and Serious Breaches of the Protocol or ICH GCP

In the event of any prohibition or restriction imposed (i.e., clinical hold) by an applicable Competent Authority, or if the investigator is aware of any new information which might influence the evaluation of the benefits and risks of the investigational product, the sponsor will be informed immediately.

In addition, the investigator will inform the sponsor immediately of any urgent safety measures taken by the investigator to protect the study subjects against any immediate hazard, and of any serious breaches of this protocol or of ICH GCP, defined as a breach that will likely affect the safety or physical or mental integrity of subjects or the scientific value of the trial, that comes to the attention of the investigator.

11.8 Study Discontinuation and Closure

The sponsor reserves the right to discontinue the study prior to inclusion of the intended number of subjects, but intends only to exercise this right for valid scientific or administrative reasons. After such a decision, the investigator will contact all participating subjects within a time period specified by the sponsor to inform them of the decision to discontinue the study.

11.8.1 Criteria for Premature Termination or Suspension of the Study

The following criteria may result in either temporary suspension or ET of the study:

- New information regarding the safety or efficacy of the study drug that indicates a change in the known risk/benefit profile for the compound, such that the risk/benefit is no longer acceptable for subjects participating in the study
- Significant violation of GCP that compromises the ability to achieve the primary study objectives or compromises subject safety
- Request from regulatory agencies

The sponsor reserves the right to discontinue the study for other valid administrative reasons. If the study has been suspended or terminated, prompt notification will be given to investigators, IRBs, and regulatory authorities in accordance with regulatory requirements.

11.8.2 Criteria for Premature Termination or Suspension of Study Sites

The Sponsor may terminate this study prematurely, either in its entirety or at any study site, for reasonable cause provided that written notice is submitted in advance of the intended

termination. Advanced notice is not required if the study is stopped due to safety concerns. If the Sponsor terminates the study for safety reasons, the Sponsor will immediately notify the Investigator and subsequently provide written instructions for study termination. If the study has been suspended or terminated, prompt notification will be given to Investigators, IRBs, and regulatory authorities in accordance with regulatory requirements.

A study site may be terminated prematurely or suspended if the study site (including the investigator) is found to be in significant violation of GCP, protocol, contractual agreement, or is unable to ensure adequate performance of the study.

The investigator will notify the sponsor if the trial is terminated by the investigator or the IRB at the site. If the investigator, IRB, or sponsor decides to terminate or suspend the trial conduct at a particular study site for safety, non-enrollment, non-compliance with the protocol, or other unanticipated reasons, the above parties will be promptly notified.

11.8.3 Criteria for Premature Termination or Suspension of the Study or Study Sites

In the event that the sponsor elects to terminate or suspend the study or the participation of an investigational study site, a study-specific procedure for ET or suspension will be provided by the sponsor; the procedure will be followed by applicable study sites during the course of termination or study suspension.

11.9 Future Use of Stored Specimens and Data

With the subject's approval and as approved by local IRBs, de-identified biological samples will be stored at the biorepository with the same goal as the sharing of data with the biorepository. These samples could be used to research the causes of anemia in subjects receiving hemodialysis in CKD, its complications and other conditions for which individuals with anemia in subjects receiving hemodialysis in CKD are at increased risk, and to improve treatment. The biorepository will also be provided with a code-link that will allow linking the biological specimens with the phenotypic data from each subject, maintaining the blinding of the identity of the subject.

During the conduct of the study, an individual subject can choose to withdraw consent to have biological specimens stored for future research. However, withdrawal of consent with regard to biosample storage may not be possible after the study is completed.

When the study is completed, access to study data and/or samples will be provided through the biorepository.

11.10 Key Roles, Committees and Study Governance

Not applicable.

11.11 Safety Oversight

An Independent Data Monitoring Committee (IDMC) will be established to review and discuss the available study data as subjects are enrolled and followed. The IDMC will meet approximately twice per year throughout the course of the study. The IDMC will be unblinded

and will include, at a minimum, 2 physicians and a biostatistician. The discussions of the IDMC will include a review of key safety data (i.e., AEs, vital sign measurements, and laboratory assessments).

AEs and laboratory changes suggestive of possible effects on the liver will be reviewed and adjudicated by a hepatic panel of experts.

11.12 Quality Assurance and Quality Control

Each clinical site will perform internal quality management of study conduct, data and biological specimen collection, documentation and completion. An individualized quality management plan will be developed to describe a site's quality management.

Quality control (QC) procedures will be implemented beginning with the data entry system and data QC checks that will be run on the database will be generated. Any missing data or data anomalies will be communicated to the site(s) for clarification/resolution.

Following written Standard Operating Procedures (SOPs), the monitors will verify that the clinical trial is conducted and data are generated and biological specimens are collected, documented (recorded), and reported in compliance with the protocol, ICH GCP, and applicable regulatory requirements (e.g., Good Laboratory Practices [GLP], GMP).

The investigational site will provide direct access to all trial related sites, source data/documents, and reports for the purpose of monitoring and auditing by the sponsor, and inspection by local and regulatory authorities.

11.12.1 Clinical Monitoring

During study conduct, the sponsor or its agent will conduct periodic monitoring visits to ensure that the protocol and GCP are being followed. The monitors will review source documents to confirm that the data recorded on the eCRFs is accurate. The investigator/institution will allow the sponsor's monitors or designees and appropriate regulatory authorities direct access to source documents to perform this verification.

The study site may also be subject to Quality Assurance audits performed by the sponsor or companies working with or on behalf of the sponsor, and/or review by the IRB, and/or to inspection by appropriate regulatory authorities.

It is important that the investigator(s) and their relevant personnel are available during the monitoring visits and possible audits or inspections and that sufficient time is devoted to the process.

11.12.2 Protocol Deviations

A protocol deviation is generally an unplanned excursion from the protocol that is not implemented or intended as a systematic change. The investigator is responsible for ensuring the study is conducted in accordance with the procedures and evaluations described in this protocol and must protect the rights, safety, and welfare of subjects. The investigator should not

implement any deviation from, or changes of, the protocol, unless it is necessary to eliminate an immediate hazard to trial subjects.

A protocol waiver is a documented prospective approval of a request from an investigator to deviate from the protocol. Protocol waivers are strictly prohibited.

For the purposes of this protocol, deviations requiring notification to sponsor are defined as any subject who:

- Entered into the study even though they did not satisfy entry criteria.
- Developed withdrawal criteria during the study and not withdrawn.
- Received wrong treatment or incorrect dose.
- Received excluded concomitant treatment.

When one of these deviations from the protocol is identified for an individual subject, the investigator or designee must ensure the sponsor is notified. If the investigator determines that the deviation impacts the safety of a subject, the investigator must contact the sponsor immediately. The sponsor will follow-up with the investigator, as applicable, to assess the deviation and the possible impact to the safety and/or efficacy of the subject to determine subject continuation in the study.

The investigator will also assure that deviations meeting IRB/IEC and applicable regulatory authorities' criteria are documented and communicated appropriately. All documentation and communications to the IRB/IEC and applicable regulatory authorities will be filed in the Investigator Site Files and will be provided to the sponsor and maintained within the Trial Master File.

Note: Other deviations outside of the categories defined above that are required to be reported by the IRB/IEC in accordance with local requirements will be reported, as applicable.

12.0 PUBLICATION OF STUDY RESULTS

No publication or disclosure of study results will be permitted, except under the terms and conditions of a separate, written agreement between sponsor and the investigator and/or the investigator's institution. The sponsor will have the opportunity to review and approve all proposed abstracts, manuscripts, or presentations regarding this study prior to submission for publication/presentation. Any information identified by the sponsor as confidential will be deleted prior to submission.

For all publications relating to the study, the institution will comply with recognized ethical standards concerning publications and authorship, including: Section II - "Ethical Considerations in the Conduct and Reporting of Research" of the Uniform Requirements for Manuscripts Submitted to Biomedical Journals, <http://www.icmje.org/index.html#authorship>, established by the International Committee of Medical Journal Editors.

AE	adverse event
AESI	adverse event of special interest
ALP	alkaline phosphatase
ALT	alanine aminotransferase
ARCRS	American Renal Clinical Research Services
AST	aspartate aminotransferase
ANCOVA	analysis of covariance
BMI	body mass index
BUN	blood urea nitrogen
CBC	complete blood count
CI	confidence interval
CKD	chronic kidney disease
CPK	creatine phosphokinase
CRO	contract research organization
CRP	C-reactive protein
CV	cardiovascular
DBP	diastolic blood pressure
DILI	drug-induced liver injury
eCRF	electronic case report form
EOT	end of treatment
EPO	erythropoietin
ESA	erythropoiesis-stimulating agent
ET	early termination
FAS	full analysis population
FCS	fully conditional specification
Hb	hemoglobin
HDL	high density lipoprotein

Abbreviation	Definition
HF	heart failure
INR	international normalized ratio
IV	intravenous
[REDACTED]	[REDACTED]
MAR	missing at random
MedDRA	Medical Dictionary for Regulatory Activities
MMRM	mixed model repeated measures
MNAR	missing not at random
LDH	lactate dehydrogenase
LDL	low density lipoprotein
LLD	lower limits of detection
MCH	mean corpuscular hemoglobin
MCHC	mean corpuscular hemoglobin concentration
MCS	mental health composite score
MCV	mean corpuscular volume
PCS	physical health composite score
PEP	primary efficacy period
[REDACTED]	[REDACTED]
[REDACTED]	[REDACTED]
PP	per protocol
PT	preferred term
RBC	red blood cell
RDW	red blood cell distribution width
SAE	serious adverse event
SAP	statistical analysis plan
SBP	systolic blood pressure
SD	standard deviation
SE	standard error
SEP	secondary efficacy period

Abbreviation	Definition
SF-12	12-Item Short Form Survey
SGPT	serum glutamic pyruvic transaminase
SOC	system organ class
TEAE	treatment-emergent adverse event
TFL	table, listing, figure
TIBC	total iron binding capacity
TIW	three times weekly
TSAT	transferrin saturation
ULN	upper limit of normal
US	United States
USRC	U.S. Renal Care
[REDACTED]	[REDACTED]
WBC	white blood cell

1. INTRODUCTION

The purpose of this statistical analysis plan (SAP) is to describe the procedures and the statistical analysis methods that will be used to analyze, and report results for Akebia Protocol AKB-6548-CI-0039.

This SAP is based on the final study protocol, version 1.0 (dated 16 September 2020). Details of study design, conduct and data collection are described in the study protocol, the electronic case report form (eCRF), and general eCRF completion guidelines. The specifications of tables, figures, and data listings are included in a separate document (i.e., TFL shells).

If the analyses described in the protocol differs from those in this SAP, the analysis methods described in the SAP prevail.

2. STUDY OBJECTIVES

2.1 PRIMARY OBJECTIVE

To demonstrate the efficacy and safety of vadadustat administered three times weekly (TIW) compared to long-acting ESA (Mircera) for the maintenance treatment of anemia in hemodialysis subjects.

3. STUDY DESIGN

3.1 OVERVIEW

This is a multi-center, randomized, open-label, active-controlled study of the efficacy and safety of conversion from long-acting ESA (Mircera) to vadadustat TIW for the maintenance treatment of anemia in hemodialysis patients. Following a Screening period of up to 8 weeks (56 days), subjects who meet all inclusion and none of the exclusion criteria will be randomized 1:1:1 to vadadustat 600 mg TIW, vadadustat 900 mg TIW, or to remain on Mircera according to the dialysis center's protocol. The planned number of subjects are 450 at approximately 60 investigative sites in the United States (US) at outpatient hemodialysis centers.

Randomization will be stratified across dialysis organization: USRC (U.S. Renal Care), ARCRS (American Renal Clinical Research Services), and Frenova (Frenova Renal Research).

Following randomization there will be 2 periods during the study:

- **Conversion and Maintenance Period (Weeks 0 to 52):** conversion to vadadustat TIW or to remain on Mircera (Weeks 0 to 20). There will be a primary efficacy

evaluation period (Weeks 20 to 26) and a secondary efficacy evaluation period (Weeks 46 to 52).

- **Safety Follow-up Period (Early Termination [ET] and Follow-Up):** post-treatment safety follow-up visit (ET/End of Treatment [EOT] +4 weeks) either in person or via telephone.

End of Study:

- **Study Completion**

[figure not shown]
The study will be considered completed after all randomized subjects have completed their final study visit (Week 52/or ET and Safety Follow-Up at Week 56).

- **Subject Completion**

Completion of treatment: A subject will be considered as having completed the study treatment after completion of their study treatment through Week 52.

Completion of study: A subject will be considered as having completed the study after completion of their study treatment through Week 52 and the safety follow-up visit.

Figure 1. Study Schema

ESA: erythropoiesis-stimulating agent; HD: hemodialysis; R: randomized; TIW: three times weekly

Dosing will be initiated at Baseline and the first dose of vadadustat will be administered at the hemodialysis unit after other Baseline procedures have been completed. Subjects randomized to vadadustat may take vadadustat with or without food and will be instructed to swallow the tablet(s) whole. Subjects are to take vadadustat at roughly the same time each day.

Mircera assigned subjects will be administered IV Mircera at the hemodialysis unit according to the dialysis center's protocol.

Dose adjustments will be guided by central laboratory Hb concentrations throughout the study to determine if vadadustat or Mircera doses will be adjusted, interrupted, or maintained. Mircera dosing will be based on standard of care laboratory measures according to the dialysis center's protocol. Vadadustat dose adjustment will be based on the guidelines in the protocol Section 7.1.2.

The minimum dose of vadadustat will be 300 mg TIW (1 tablet TIW) and the maximum dose will be 1200 mg TIW. Subjects whose dose of vadadustat is interrupted due to elevated Hb will continue in the study. Unless contraindicated, treatment will be resumed whenever possible and assessed at every study visit following study drug interruption.

Clinical evaluations will be conducted during the course of the study based on the schedule of activities in the protocol Table 1. If the evaluations will occur on a hemodialysis day, the clinical evaluations should be completed before dialysis, if applicable.

3.2 STUDY POPULATION

The study population will consist of subjects greater than or equal to 18 years of age who are receiving chronic, outpatient in-center hemodialysis three times weekly (TIW), requiring erythropoiesis-stimulating agent (ESA) treatment and are on maintenance treatment with Mircera. Study subjects will also be required to have a mean Screening hemoglobin (Hb), based on 2 results, between 8.5 and 11.0 g/dL (inclusive).

3.3 SAMPLE SIZE DETERMINATION

For the primary efficacy analysis, it is assumed that the difference in mean change from Baseline in Hb for vadadustat will be the same as the active control, Mircera, and the common standard deviation for the mean change from Baseline will be assumed to be 1.2 g/dL. The noninferiority margin of -0.75 g/dL will be used (for vadadustat minus Mircera). With the 1:1:1 randomization ratio of vadadustat 600 mg TIW, vadadustat 900 mg TIW, and Mircera, and approximately 150 subjects in each arm, the noninferiority test will have >90% power with consideration of a 30% drop out rate.

3.4 STUDY MEDICATION STOPPING RULES

Vadadustat must be permanently discontinued if a subject meets 1 of the following criteria:

- ALT or AST >3x ULN and total bilirubin >2x ULN
- ALT or AST >3x ULN and international normalized ratio (INR) >1.5
- ALT or AST >8x ULN
- ALT or AST remains >5x ULN over 2 weeks (re-challenge generally should be avoided with ALT or AST >5x ULN unless there are no other good therapeutic options)

-
- ALT or AST >3x ULN with symptoms (e.g., fatigue, nausea, vomiting, right upper quadrant pain, fever, rash) or eosinophilia
 - undergo a solid organ (including kidney), hematopoietic stem cell, or bone marrow transplantation

3.5 MEASURES TO MINIMIZE BIAS: RANDOMIZATION AND BLINDING

This will be an open-label study. Treatment assignment will be done through a validated electronic system by block randomization with a block size of 6. Treatments will be administered in an open-label fashion. The sponsor study team will be blinded to ‘by treatment’ aggregated analyses except for the unblinded statistician. This will be detailed in a separate document of “Blinding Plan”.

In addition, the study involves the use of an Independent Data Monitoring Committee (IDMC), and an identical schedule of visits, procedures, and assessments for all treatment groups in order to reduce the potential bias. An external independent group of unblinded biostatisticians and programmers will provide the support to IDMC.

4. ANALYSIS POPULATION

The following analysis populations will be used in this study:

- Randomized population: defined as all randomized subjects. This population will be analyzed based upon the randomized treatment. This is the Intention to Treat (ITT) population.
- Full analysis population (FAS): defined as randomized subjects receiving 1 or more doses of study medication and had at least one post-dose Hb assessment. This population will be analyzed based upon the randomized treatment.
- Per protocol (PP) population: defined as all randomized subjects who received study medication during the primary evaluation period, had at least 1 Hb assessments during the primary evaluation period, and have no important protocol deviations affecting the primary endpoint analyses, i.e., up to Week 26. This population will be analyzed based upon the actual treatment received. Protocol deviations leading to exclusion from the PP population will be specified prior to database lock on a blinded basis and recorded in a separate document.
- Safety population: defined as all subjects who received at least 1 dose of study medication. This population will be analyzed based upon the actual treatment received. Subjects who received in error some vadadustat and some Mircera (excluding rescue therapy) will be classified by the more frequently received drug.

Efficacy analyses will utilize the randomized/ITT, full analysis (FAS), and PP populations while safety analyses will utilize the safety population.

5. ENDPOINTS

5.1 PRIMARY EFFICACY ENDPOINT

Mean change in Hb between Baseline (average of the last 2 available pretreatment Hb) and the primary evaluation period (average Hb from Weeks 20 to 26, inclusive).

5.2 SECONDARY EFFICACY ENDPOINT

Mean change in Hb between Baseline (average of the last 2 available pretreatment Hb) and the secondary evaluation period (average Hb from Weeks 46 to 52, inclusive).

5.3 OTHER EFFICACY ENDPOINTS

Other endpoints include the following:

- Proportion of subjects having a Hb value within the target range (10.0 to 11.0 g/dL) during the primary evaluation period (Weeks 20 to 26).
- Proportion of subjects having a Hb value within the target range (10.0 to 11.0 g/dL) during the secondary evaluation period (Weeks 46 to 52).
- Proportion of subjects having average Hb value within the target range (10.0 to 11.0 g/dL) during the primary evaluation period (Weeks 20 to 26)
- Proportion of subjects having average Hb value within the target range (10.0 to 11.0 g/dL) during the secondary evaluation period (Weeks 46 to 52)
- Mean change from baseline and percentage change from baseline in the primary efficacy period (PEP) and secondary efficacy period (SEP) for iron-related parameters
- Proportion of subject receiving rescue by analysis periods.
- Proportion of subjects receiving RBC transfusions by analysis periods.
- Proportion of subjects receiving ESA medication by analysis periods.
- Time to first rescue by narrow and broad (include any rescue, ESA, and RBC respectively)
- Proportion of subjects who received any IV iron therapy by analysis period)
- Mean weekly IV dose elemental iron by analysis period and route of administration
- Mean change in serum glucose and lipid parameters between Baseline and the PEP (Weeks 20 to 26) and SEP (Weeks 46 to 52)
- Mean change in iron metabolism (including iron, hepcidin, ferritin, transferrin saturation [TSAT], total iron binding capacity [TIBC]) between Baseline and the PEP (Weeks 20 to 26) and SEP (Weeks 46 to 52)

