4.7 Secondary Safety Endpoints

Secondary endpoints include the following:

- Proportion of subjects receiving RBC transfusions from Baseline to Week 26.
- Proportion of subjects receiving RBC transfusions from after Week 26 to Week 52.
- Proportion of subjects with Hb >11.0, Hb >12.0, >13.0, or >14.0 g/dL.
- Proportion of subjects with Hb <7.0, <8.0, <9.0, or <10.0 g/dL.
- Proportion of subjects with Hb increase >1.0 g/dL within any 2-week interval or >2.0 g/dL within any 4-week interval.

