10.5.5 Safety Analyses

All analyses of safety data will use the safety population.

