5.5 SECONDARY SAFETY ENDPOINTS

Secondary endpoints include the following:

- Proportion of subjects with Hb >11.0, Hb >12.0, >13.0, or >14.0 g/dL.
- Proportion of subjects with Hb <7.0, <8.0, <9.0, or <10.0 g/dL.
- Proportion of subjects with Hb increase >1.0 g/dL within any 2-week interval or >2.0 g/dL within any 4-week interval.

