6.2 VISIT AND ANALYSIS TIME PERIOD CLASSIFICATION

All assessments will be mapped to the corresponding analysis visit (i.e., target week) based on study day, including unscheduled visits. [Table 1](#) is a general window for each visit based on the protocol. [Table 2](#) will be applied for less frequent assessments such as

[REDACTED] C-Reactive Protein (CRP), Complete Blood Count (CBC) with differential, Serum Chemistry, Lipid Panel, Reticulocyte count, Biomarkers, Erythropoietin and Dialysis Adequacy. All other assessments will apply to the analysis window from Table 1.

If more than one Hb assessment is available in a post-baseline analysis period (i.e., PEP or SEP), then all results will be used to calculate the average of Hb. But if more than one record is available in same day, the last assessment (i.e., at most one record per day) will

be used to calculate the average. For other assessments, if more than one assessment is available in each window, the assessment which is closest to the target day will be used for analysis. If the assessments are equally close, the last assessment will be used.

Table 1. Classification of Assessments at Every Visit (General)

Analysis Time Period	Visit	Target Day	Analysis Window
Baseline	Screening Visit 1	-	-
	Screening Visit 2	-	-
Week 2-6	Baseline	Day 1	<=Day 1 (prior to first dose) ^a
	Week 2	Day 14	Day 1 (post dose) – 21
	Week 4	Day 28	Day 22 – 35
Week 8-16	Week 6	Day 42	Day 36 – 49
	Week 8	Day 56	Day 50 – 70
	Week 12	Day 84	Day 71 – 98
Primary Efficacy Period (PEP) (Weeks 20-26)	Week 16	Day 112	Day 99 – 126
	Week 20	Day 140	Day 127 – 154
	Week 24	Day 168	Day 155 – 175
Week 30-42	Week 26	Day 182	Day 176 – 196
	Week 30	Day 210	Day 197 – 224
	Week 34	Day 238	Day 225 – 252
	Week 38	Day 266	Day 253 – 280
Secondary Efficacy Period (SEP) (Weeks 46-52)	Week 42	Day 294	Day 281 – 308
	Week 46	Day 322	Day 309 – 336
	Week 50	Day 350	Day 337 – 357
Safety Follow-up ^b	Week 52	Day 364	Day 358 – 378 or ET/EOT assessment date + 15 days
	Follow-up	ET/EOT assessment date + 28 days	>= ET/EOT assessment date + 15 days

^a If patient has no first dose date, day 1 will be the randomization date.

^b for Vital Sign, Dialysis Access Type, and Therapeutic Phlebotomy

Table 2. Classification of Assessments for Selected Assessment

Analysis Time Period	Visit	Target Day	Analysis Window
Baseline	Screening Visit 1	-	-
	Screening Visit 2	-	-
	Baseline	Day 1	<=Day 1 (prior to first dose) ^a
Week 2-6	Week 4	Day 28	Day 1 (post dose) – 49

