6.11.4.4 Definition of Rescue

The eCRF collects reasons for ESA medication and RBC transfusion. An Event is considered as rescue only when the event occurred between first dose date to permanent study treatment discontinuation. The series of rescue definitions are defined as follows:

- Narrow:
 - For RBC transfusion, when “Low Hemoglobin” is the reason indicated on the eCRF.
 - For ESA medication:
 - Vadadustat arm: the reason of ESA usage is the subject’s Hb less than 9.0 g/dL.
 - Mircera arm: two scenarios are defined as below:
 - i. the reason of other ESA or Mircera usage is the subject’s Hb less than 9.0 g/dL or Mircera dose increase at least 50%.
 - ii. the reason of other ESA or Mircera usage is the subject’s Hb less than 9.0 g/dL or Mircera dose increase at least 100%.
- Broad:
 - Any RBC transfusion.
 - For ESA medication:
 - Vadadustat arm: any ESA usage.
 - Mircera arm: two scenarios are defined as below:
 - i. Any other ESA usage, or Mircera usage due to the subject’s Hb less than 9.0 g/dL or Mircera dose increase at least 50%.
 - ii. Any other ESA usage, or Mircera usage due to the subject’s Hb less than 9.0 g/dL or Mircera dose increase at least 100%.

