7. CHANGES TO PROTOCOL-PLANNED ANALYSES

Removed the hierarchical testing scheme for both primary and secondary efficacy endpoints. Treatment comparisons will be performed between vadadustat (combining the 2 randomized groups with starting dose of 600mg and 900mg) and Mircera groups. Subjects in the vadadustat starting dose groups of 600 mg or 900 mg TIW will have their doses adjusted to maintain Hb levels of 10.0 to 11.0 g/dL following the protocol's dosing algorithm. The subgroup analysis with different starting dose with vadadustat vs. Mircera will be considered as exploratory analyses.

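### The protocol's two RBC-transfusion secondary safety endpoints are missing from the SAP's safety endpoints, and the by-period rescue summary put in their place does not yield them

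*SAP*

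**What the plan says.** Protocol 4.7, Secondary Safety Endpoints, lists "Proportion of subjects receiving RBC transfusions from Baseline to Week 26" and "Proportion of subjects receiving RBC transfusions from after Week 26 to Week 52". The synopsis lists the same two items among the safety endpoints. Protocol 10.5.5 fixes the population: "All analyses of safety data will use the safety population". Protocol 10.5.7 leaves the detailed analysis of the safety endpoints to the SAP.

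SAP 5.5 carries over the other three items of Protocol 4.7: the high Hb thresholds, the low Hb thresholds, and "Proportion of subjects with Hb increase >1.0 g/dL within any 2-week interval or >2.0 g/dL within any 4-week interval". It omits both transfusion items. SAP 5.4, 5.6 and the visible text of 6.12 have no transfusion analysis either.

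Transfusion appears in SAP 5.3, among the other efficacy endpoints, as "Proportion of subjects receiving RBC transfusions by analysis periods". SAP 6.11.4.4.2 sends it through the rescue analyses, under a narrow definition (reason recorded as low hemoglobin) and a broad one (any RBC transfusion). SAP 6.11.4.4 limits what counts: "An Event is considered as rescue only when the event occurred between first dose date to permanent study treatment discontinuation". SAP 6.11.4 makes the randomized population the default for other efficacy analyses.

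SAP section 7, on changes from the protocol, opens with "Removed the hierarchical testing scheme for both primary and secondary efficacy endpoints" and goes on to the pooling of the two vadadustat groups. It does not mention transfusion. SAP section 1 says that the SAP's analysis methods prevail where the two documents differ.

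**The concern.** Two safety endpoints specified in the protocol have lost their safety status, their time windows and their analysis population, with no declared change. An analyst who follows the visible SAP would produce neither proportion.

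This matters because Protocol 5.2 cites labelling that ties ESA dosing to the avoidance of transfusion. In addition, Protocol 9.11.1.1 does not treat worsening anemia as an adverse event unless its cause is something other than the subject's CKD. The adverse event tables will therefore largely miss loss of response that leads to transfusion. The low-Hb endpoints cover part of that ground, but they do not record whether blood was given.

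**Working it through.** The documents state no transfusion rate and no sample size for this endpoint, so there is no figure of the plan's own to reproduce. The check compares windows and then asks what can be recovered from the period percentages.

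**Step 1. Windows.** The day ranges come from SAP Table 1 (section 6.2). The last window also has an alternative end tied to the ET/EOT date.

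| SAP analysis period | Days | Cut at the Week 26 visit window (Day 196/197) | Cut at nominal Week 26 (Day 182/183) |
|---|---|---|---|
| Weeks 2-6 | 1-49 | first protocol window | first |
| Weeks 8-16 | 50-126 | first | first |
| Weeks 20-26 (PEP) | 127-196 | first | straddles both |
| Weeks 30-42 | 197-308 | second | second |
| Weeks 46-52 (SEP) | 309-378 | second | second, running past Day 364 |

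No single period equals either protocol window. By visit windows, Baseline to Week 26 is the union of the first three periods (Day 1-196), and after Week 26 to Week 52 is the union of the last two (Day 197-378).

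**Step 2. From period percentages to a window proportion.** Let p_i be the proportion transfused in period i, on a common denominator. The proportion transfused at least once over the window then satisfies

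max(p_i) ≤ P(any) ≤ min(1, Σp_i),

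and equals 1 − Π(1 − p_i) if the periods are independent. The lower bound applies when the same subjects are transfused each time, and the upper bound when they are all different.

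Take an assumed 4% in each of the first three periods:
- lower bound: 4%
- upper bound: 3 × 4% = 12%
- independence: 1 − 0.96³ = 11.5%

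Other assumed rates, using the same formulas:

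| Assumed rate per period | Baseline to Week 26 (3 periods) | Under independence | After Week 26 to Week 52 (2 periods) | Under independence |
|---|---|---|---|---|
| 1% | 1-3% | 3.0% | 1-2% | 2.0% |
| 2% | 2-6% | 5.9% | 2-4% | 4.0% |
| 3% | 3-9% | 8.7% | 3-6% | 5.9% |
| 5% | 5-15% | 14.3% | 5-10% | 9.8% |

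These are bounds under assumed rates and not forecasts. They show that two arms could have identical period percentages and different window proportions. At 4% per period the extreme gap is 12% − 4% = 8 points.

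**Step 3. The time-to-event analysis.** SAP 6.11.4.4.1, applied to transfusion by 6.11.4.4.2, plans Kaplan-Meier, log-rank and Cox analyses of time to first event, with subjects without an event censored at last dose. Under the broad definition the curve can be read at Week 26. That is a censored cumulative estimate and a different statistic from the crude proportion. It cannot give the second endpoint: a subject transfused at Week 10 and again at Week 40 belongs in both protocol proportions but leaves the risk set at Week 10.

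**Step 4. Population.** Rescue counting starts at first dose. In the randomized population, a never-dosed subject is in the denominator but cannot have an event. The safety population in the protocol excludes such subjects.

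**The case against.** The strongest reply is that little is lost. The subject-level data exist, and the Table 1 periods divide cleanly at the Week 26 visit window, so both proportions are a regrouping of flags already derived. SAP 6.11.4.4.1 already specifies proportions, 95% CIs, differences, odds ratios and stratified Mantel-Haenszel. The table shells are a separate document and parts of the SAP are redacted, so a cumulative row may be planned there. The protocol attaches no hypothesis, margin or power to this endpoint. All of this stands, and it limits the point to one of specification and reporting. It does not remove the conflict: the visible SAP text defines different endpoints, under a different heading, and does not say so.

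A reader might infer more, in three ways that the documents do not support:

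- *That cumulative transfusion risk is hidden.* It is not, because a Kaplan-Meier curve for time to first RBC transfusion is planned.
- *That transfusions in the 4 weeks after stopping drug must be added.* Protocol 4.7 does not ask for this. Under Protocol 8.1.2, subjects who stop leave the study apart from an ET visit and a 4-week follow-up, and the Schedule of Activities calls for transfusions to be documented during the Treatment Period. Whether they are fully captured afterwards is unclear, and the on-treatment limit probably matters little.
- *That a precision calculation shows the endpoint to be informative.* At an assumed 10% rate with 300 against 150 subjects, the 95% half-width is 1.96 × √(0.1 × 0.9 × (1/150 + 1/300)) = 5.9 points. The rate is an assumption, the 30% drop-out is ignored, and no target difference is stated against which to judge 5.9 points.

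**Conclusion.** The protocol and the SAP conflict on two specified secondary safety endpoints. On the visible text, the SAP drops both from its safety sections and replaces them with an on-treatment rescue summary by period, in another default population and without declaring the change. The period percentages do not determine the protocol proportions, and the time-to-first-event analysis covers the first window only in part and the second not at all.

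The possible gap between period and window figures depends on rates that the documents do not give. With 1% to 5% per period it runs from 1-3% up to 5-15% for the first window, and from 1-2% up to 5-10% for the second, assuming a common denominator across periods. The conflict itself does not depend on those rates. No data are lost and no confirmatory test is affected. The redacted SAP material and the table shells could not be checked.

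**What to change.** 1. Restore both proportions to SAP 5.5 and 6.12 as secondary safety endpoints in the safety population.
2. Count any RBC transfusion (the broad definition), once per subject per window. State the windows in days: by the SAP's visit windows, Day 1-196 and Day 197-378.
3. Report the proportion in each group, and the difference with its 95% CI from the Mantel-Haenszel method stratified by dialysis organization, as already planned.
4. Keep the by-period and time-to-first-transfusion rescue analyses as supportive.
5. List in SAP section 7, with reasons, any departure from Protocol 4.7 that remains, including the limit to first dose through permanent discontinuation if it is kept.

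The cost is SAP wording and two table rows. No new data collection is needed for transfusions during the treatment period.
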